6.2 SUMMARIES OF CONDUCT OF STUDY

The number of patients who are randomized, enroll, discontinue, or complete the study will be summarized. Reasons for premature study discontinuation will be listed and summarized.

Eligibility criteria and other major protocol deviations will be listed and summarized by treatment group.

6.3 SUMMARIES OF DEMOGRAPHIC AND BASELINE CHARACTERISTICS

Demographic and baseline characteristics (including, but not limited to, age, sex, race, onset of symptoms, baseline symptom severity, presence of underlying health conditions, pre-existing symptoms) will be summarized using means, standard

deviations, medians, and ranges for continuous variables and proportions for categorical variables, as appropriate. Summaries will be presented by treatment group and will be presented for the mITTi population and may, in addition, be presented for the safety population.

Medical history data, including surgery and procedures, and baseline conditions, will be summarized descriptively by treatment group using the safety population. Previous and concomitant treatments will be summarized descriptively by treatment group. Exposure to study drug will be summarized, including number of doses. A listing of patients by treatment group, detailing dosing of study drug will be prepared.

6.4 VIROLOGY AND EFFICACY ANALYSES

All virology and efficacy analyses will be performed on the mITTi population.

Sensitivity analyses to evaluate the robustness of results to the primary analysis methods (e.g., handling of dropouts) may be conducted and will be described in the SAP.

No alpha adjustments for multiple comparisons are planned.

6.4.1 Primary Virology Endpoint

The primary objective of this study is to evaluate the antiviral activity of AT-527 compared with placebo on the basis of the change from baseline in amount of SARS-CoV-2 virus RNA as measured by RT-PCR and based on the log-10 scale at specified timepoints.

In Cohorts A-D, the change from baseline in the amount of SARS-CoV-2 virus RNA will be compared between each AT-527 group and a combined placebo group at Days 3, 5, and 7 using Analysis of Covariance (ANCOVA) with baseline virus RNA as a covariate. The treatment group least squares mean (LSM) changes, difference in LSM changes, 80% CI and p-value will be presented for each comparison. Additionally, descriptive summaries for the change from baseline will also be presented by treatment group.

In Cohort E, the change from baseline in the amount of SARS-CoV-2 virus RNA will be compared between the AT-527 group and a placebo group containing only patients from Cohort E (unpooled) at Days 3, 5, 7, and 14 using Analysis of Covariance (ANCOVA) with baseline virus RNA as a covariate. The treatment group least squares mean (LSM) changes, difference in LSM changes, 95% CI and p-value will be presented for each comparison. Additionally, descriptive summaries for the change from baseline will also be presented by treatment group.

If the data are not normally distributed, a non-parametric alternative method will be used (e.g., Mann-Whitney U test) to compare distributions.

Further details of the primary endpoint analysis will be included in the SAP, including details of any missing data handling rules for the primary endpoint.

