6. STATISTICAL CONSIDERATIONS AND ANALYSIS PLAN

All primary and secondary virology and efficacy outcomes will be analyzed in the modified intent-to-treat infected (mITTi) population. The mITTi population is defined as all patients randomized in the study who received any amount of study drug and had at least one positive SARS-CoV-2 RT-PCR test result *above or equal to the limit of quantification (LOQ)* during the study, with patients grouped according to the treatment assignment at randomization.

Safety analyses will be performed on the safety evaluable population, which consists of all patients who receive any amount of study drug. In all safety analyses, patients will be grouped according to the treatment that the patients actually received rather than the treatment assigned at randomization.

For *Cohorts A–D*, the primary virology analysis will be performed as part of a Day 10 review (accompanied with key safety review if deemed necessary, further details will be included in the SAP) which is to be completed after all patients enrolled in the current cohort have completed assessments through Day 10. Other endpoints will be analyzed at the completion of each full cohort or at the completion of the study.

For *Cohorts A–D*, all analyses at the Day 10 review or at the completion of each cohort will compare each AT-527 dose group and a combined placebo group, including all placebo patients enrolled across cohorts up to the cohort being analyzed, while analyses performed at the completion of the study will compare each AT-527 dose group and a combined placebo group from *Cohorts A–D*.

For *Cohort E*, the primary virology analysis will be performed as part of a Day 14 review (accompanied with key safety review if deemed necessary, further details will be included in the SAP) which is to be completed after all patients in *Cohort E* have completed assessments through Day 14. Other endpoints will be analyzed at the completion of the cohort.

For *Cohort E*, all analyses will compare the AT-527 dose group and the placebo group from *Cohort E* only. Data from cohorts with the same dose may be pooled to further evaluate the primary endpoint as part of a sensitivity analysis. Full details of all planned tables, listings, graphs, and statistical methods will be provided in a Statistical Analysis Plan (SAP), which will be finalized prior to the end of the study.

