6.1 DETERMINATION OF SAMPLE SIZE

The primary objective of this study is to evaluate the antiviral activity of AT-527 compared with placebo. Approximately 60 patients will be randomized in a 1:1 ratio in Cohort A to receive AT-527 or placebo. Cohorts B–D will enroll approximately 40 patients in a 3:1 ratio to receive AT-527 or placebo, respectively. *Cohort E will enroll approximately 224 patients in a 1:1 ratio to receive AT-527 or placebo.*

The sample size for Cohort A–D is based on the primary endpoint of change from baseline in SARS-CoV-2 virus RNA measured by RT-PCR at a single timepoint. A sample size of 27 patients per arm (active or placebo) in the mITTi population will result in at least 80% power to detect a mean reduction in change from baseline of between 0.7 and 1.1 log₁₀ copies using a two-sample t-test for comparison of means, assuming a standard deviation of between 1.2 and 1.85 (Regeneron 2020) and based on a 1-sided 10% alpha. The sample size has been adjusted to 30 patients per arm to account for an estimated 90% SARS-CoV-2 positive rate and is based on a single-cohort comparison of AT-527 versus placebo.

For Cohort E, a sample size of 100 patients per arm (active or placebo) in the mITTi population will result in at least 80% power to detect a mean reduction in change from baseline of 0.5 log₁₀ copies using a two-sample t-test for comparison of means, assuming a standard deviation of 1.25 (deemed appropriate based on current data from WV43042) and based on a 1-sided 2.5% alpha. The sample size for Cohort E has been adjusted to 112 patients per arm to account for an estimated 90% SARS-CoV-2 positive rate. Based on emerging external data on direct acting antivirals in COVID-19 (Fischer et al 2021), a lower mean reduction in change from baseline of 0.5 log₁₀ copies has been utilized in Cohort E. A lower alpha level has also been selected to reduce the likelihood of a false positive result and enable a more robust evaluation of the antiviral activity of AT-527 at the selected dose regimen. This sample size also allows for a better characterization of the secondary endpoints.

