6.8.2 Optional Interim Analysis

Given the hypothesis-generating nature of this study, the Sponsor may choose to conduct additional interim analyses (i.e., beyond what is specified in Section 6.8.1). The decision to conduct an optional interim analysis and the timing of the analysis will be documented in the Sponsor's trial master file prior to the conduct of the interim analysis. The interim analysis will be performed and interpreted by members of the Sponsor study team and appropriate senior management personnel, who will be unblinded at the treatment group level. Access to treatment assignment information will follow the Sponsor's standard procedures.

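### Cohort E tests its primary endpoint at four unranked visits with no deciding visit or success rule, so the error rate and power of its overall conclusion are undetermined

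*Protocol*

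**What the plan says.** Protocol 6.4.1 compares the Cohort E arms against "a placebo group containing only patients from Cohort E (unpooled) at Days 3, 5, 7, and 14 using Analysis of Covariance (ANCOVA"), with baseline viral RNA as covariate. For these comparisons the "difference in LSM changes, 95% CI and p-value will be presented for each comparison". The section ranks no visit above another and states no significance threshold. It adds that "Further details of the primary endpoint analysis will be included in the SAP".

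Protocol 6.4 states: "No alpha adjustments for multiple comparisons are planned".

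Protocol 6.1 sizes Cohort E on one two-sample t-test: 100 evaluable patients per arm, a difference of 0.5 log10 copies, SD 1.25, at least 80% power, "and based on a 1-sided 2.5% alpha". The visit is not named. The reason given for the tighter level is: "A lower alpha level has also been selected to reduce the likelihood of a false positive result".

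Protocol 6 says that for Cohort E "the primary virology analysis will be performed as part of a Day 14 review". Protocol 6.8.2 justifies optional interim analyses with the words "Given the hypothesis-generating nature of this study".

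The supplied SAP predates the Cohort E redesign. Its Section 1.2 has Cohort E as one of several 40-patient cohorts randomized 3:1, and its Section 5.3.1 tests every cohort at one-sided 10% on Days 3, 5 and 7. It also ranks no visits.

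**The concern.** One significance level and one power figure describe one test. Cohort E has four tests under the primary heading, all of equal standing, and the plan does not say how they combine into a conclusion. Three readings are open: one visit decides, any significant visit is enough, or all four must be significant. Each gives a different false-positive rate and a different power.

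This matters more in Cohort E than in the earlier cohorts, because the sponsor enlarged it and tightened its alpha specifically to make a false positive less likely. If the rule is settled only after the results are seen, nobody can say afterwards what error rate the Cohort E conclusion carried. A mixed result, significant at one or two visits, is where the ambiguity would bite.

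**Working it through.** **Inputs from Protocol 6.1, 6.4 and 6.4.1:** difference 0.5 log10 copies; SD 1.25; 100 evaluable per arm; one-sided alpha 2.5%; 90% positivity rate; four visits; no adjustment.

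**Assumptions, not in the documents:** the correlation ρ between test statistics at different visits (range 0 to 0.9); 80% power at every visit, meaning a 0.5 log10 effect at all four; and each visit tested at the full 2.5%. The last is inferred from the sample-size alpha, the 95% CIs and the no-adjustment statement.

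**Step 1: reproduce the plan's figure.** Noncentrality = 0.5 / (1.25 × √(2/100)) = 2.828, with 198 degrees of freedom. Power of the one-sided 2.5% t-test is 80.4% at 100 per arm (79.97% at 99). Inflation: 100 / 0.9 = 111.1, rounded up to 112 per arm, or 224 in total. The stated sample size is correct for one comparison. Section 6.1 states the single-timepoint basis only for Cohorts A–D; for Cohort E it follows from the single t-test.

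**Step 2: independent visits (ρ = 0).**
- Any visit counts: false-positive rate 1 − 0.975⁴ = 9.6% (upper bound 4 × 2.5% = 10%); power 1 − 0.2⁴ = 99.8%.
- All four required: false-positive rate 0.025⁴, effectively zero; power 0.8⁴ = 41%.

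**Step 3: correlated visits.** With equal correlation ρ, c = 1.96, and μ = 0 under the null or μ = 1.96 + 0.84 = 2.80 under the alternative:
- P(any) = 1 − ∫ Φ((c − μ − √ρ·u)/√(1−ρ))⁴ φ(u) du
- P(all) = ∫ [1 − Φ((c − μ − √ρ·u)/√(1−ρ))]⁴ φ(u) du

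| ρ (assumed) | Any visit: false-positive | Any visit: power | All four: false-positive | All four: power |
|---|---|---|---|---|
| 0 | 9.6% | 99.8% | <0.1% | 41% |
| 0.5 | 7.8% | 97% | <0.1% | 56% |
| 0.7 | 6.5% | 94% | 0.3% | 62% |
| 0.8 | 5.7% | 92% | 0.5% | 66% |
| 0.9 | 4.7% | 88% | 0.9% | 70% |

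If correlation instead decays with the days between visits (ρ per two days), the any-visit false-positive rate is 8.8% at 0.5 and 7.1% at 0.8, and all-visit power is 48% and 58%. These lie inside the ranges above.

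**Step 4: one named visit.** The false-positive rate is 2.5% and power 80.4% at 100 per arm, whatever the correlation.

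**The case against.** The strongest reply is that the plan is open about what it does. The absence of adjustment is stated, this is a Phase II study called hypothesis-generating, and Section 6.4.1 commits to estimates with intervals at each visit rather than to a pass or fail test. For a viral-kinetics profile, a single deciding visit is partly a matter of preference. This stands and lowers the weight of the point. It does not remove it: the endpoint is labelled primary, and disclosing no adjustment does not say which result decides.

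A reader might infer that the protocol promises a familywise 2.5% for Cohort E and breaks that promise. The text does not support this. It says only that a lower alpha was chosen to make a false positive less likely, and the preceding level is the 10% for Cohorts A–D. Under the same rule Cohort E is stricter: with any visit counting and independent visits, 1 − 0.9³ = 27.1% over three visits at 10%, against 9.6% over four visits at 2.5%.

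A reader might also infer that the stated alpha and power both fail. They do not fail under the same rule. Counting any visit raises the error rate but also raises power when the effect is present throughout; requiring all four lowers power but keeps the error rate below 1%.

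Nor does the Day 14 review make Day 14 the deciding visit. It fixes when the analysis is run; Section 6.4.1 still lists four visits equally.

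Finally, details are deferred to the SAP, which Protocol 6 says will be finalized before the study ends. Because the supplied SAP predates the redesign, its silence does not show that a Cohort E SAP would lack a rule. That is fair, and it means the SAP is a proper place for the remedy.

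**Conclusion.** The point holds as a cheap improvement. The Cohort E sample size is arithmetically right for one comparison at one visit. What is missing is the rule linking four co-equal comparisons to one conclusion, so the overall error rate and power are undetermined rather than wrong. Across the readings the documents leave open, the one-sided false-positive rate could lie anywhere from below 1% to about 10%, and power from about 41% to 99.8%.

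These ranges rest on an assumed correlation and on equal 80% power at every visit. The documents tie the 0.5 log10 target to no visit, so the multi-visit power figures are illustrative. The planned ANCOVA may be somewhat more powerful than the t-test, which does not alter the point.

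**What to change.** Before any unblinded Cohort E results are available, including from an optional interim analysis under Protocol 6.8.2, name one primary visit for Cohort E, chosen by the sponsor, and assign it the one-sided 2.5%. Report the other three visits with the same least squares mean differences and CIs as supportive, or test them in a fixed sequence after the primary visit.

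Since Protocol 6.4.1 already sends further primary-endpoint detail to the SAP, the rule can go into the SAP update for Cohort E, with 6.4.1 aligned at the next amendment.

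The cost is wording: no patients are added and no analysis is dropped. The real downside is that a significant result at a non-primary visit alone would not meet the primary endpoint.

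Splitting alpha equally over the four visits is much dearer. At 2.5% / 4 = 0.625% each, per-visit power at 100 per arm falls from 80.4% to 62%. Restoring 80% takes 141 evaluable per arm; 141 / 0.9 = 156.7, so 157 randomized per arm and 314 in total instead of 224.

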6.4.2 Secondary Virology and Efficacy Endpoints

The following virology and efficacy secondary endpoints will be compared between each AT-527 dose group and the pooled placebo group *for Cohorts A–D and an unpooled placebo group for Cohort E*:

6.4.2.1 Secondary Virology Endpoints

- Time to cessation of SARS-CoV-2 viral shedding as measured by RT-PCR
- Time to sustained non-detectable SARS-CoV-2 virus RNA
- Proportion of patients positive for SARS-CoV-2 virus RNA by RT-PCR at specified timepoints
- Area under the curve in the amount of SARS-CoV-2 virus RNA as measured by RT-PCR

6.4.2.2 Secondary Efficacy Endpoints

- Time to alleviation or improvement of COVID-19 symptoms (Items 1–12 of the COVID-19 Symptom Diary) maintained for a duration of 21.5 hours (24 hours minus 10%, to allow some flexibility in the timing of assessments), defined as follows:
 - For new symptoms: time from start of treatment to the alleviation of COVID-19 symptoms (i.e., a score of 0 [none] or 1 [mild] on the COVID-19 Symptom Diary)
 - For pre-existing symptoms: time from start of treatment to when a patient's symptoms have been maintained or improved (note improved requires at least a single category improvement from baseline on the Likert scale)

The efficacy endpoint definition includes both alleviation of new COVID-19 symptoms and maintenance/improvement of pre-existing COVID-19 symptoms to allow for the possibility that some patients may have underlying health conditions with symptoms similar to those observed with COVID-19 (e.g., cough in a patient with chronic obstructive pulmonary disease). At screening, patients will be assessed with a 14-item COVID-19 symptom severity assessment to identify pre-existing symptoms (within the prior 30 days), and assess if they worsened due to COVID-19. Symptoms that are not pre-existing are considered to be new symptoms and need to achieve sustained alleviation (score of 0 or 1) to meet the endpoint.

If a symptom is pre-existing, the patient is asked if the severity at screening is worse than what was experienced within the last 30 days prior to COVID-19:

- If the severity is not worse, the symptom must be maintained (no worsening) or improved to meet the endpoint.
- If the severity is worse, then a sustained improvement of at least one grade must be achieved to meet the endpoint. For example, a symptom classed as

severe at screening must improve to moderate, mild, or none, and a symptom classed as moderate at screening must improve to mild or none.

- The time to alleviation or improvement of COVID-19 symptoms (Items 1–12 of the COVID-19 Symptom Diary) maintained for a duration of 43 hours, defined as follows:
 - For new symptoms: time from start of treatment to the alleviation of COVID-19 symptoms (i.e., a score of 0 [none] or 1 [mild] on the COVID-19 Symptom Diary)
 - For preexisting symptoms: time from start of treatment to when a patient's symptoms have been maintained or improved (Note: Improved requires at least a single category improvement from baseline on the Likert scale.)
- Time to alleviation of COVID-19 symptoms, defined as the length of time taken from start of treatment to the point at which the following criterion is met and maintained for at least 21.5 hours: Score of 0 or 1 on Items 1–12 of the COVID-19 Symptom Diary (without consideration for presence of pre-existing symptoms)
- Time to alleviation of COVID-19 symptoms, defined as the length of time taken from start of treatment to the point at which the following criterion is met and maintained for at least 43 hours: Score of 0 or 1 on Items 1–12 of the COVID-19 Symptom Diary (without consideration for presence of pre-existing symptoms)
- Duration of fever, defined as the time to return to an afebrile state (temperature $\leq 37.5^{\circ}\text{C}$) maintained for at least 21.5 hours
- Frequency of COVID-19-related complications (death, hospitalization, radiologically confirmed pneumonia, acute respiratory failure, sepsis, coagulopathy, pericarditis, myocarditis, cardiac failure)
- *Frequency of hospitalizations and death (all cause)*
- Time to alleviation of an individual symptom, defined as the time taken from the start of treatment to the point at which the following criterion is met and maintained (for each individual symptom) for at least 21.5 hours:
 - Score of 0 or 1 for Items 1–12 of the COVID-19 Symptom Diary
 - Score of 0 for Items 13 and 14 of the COVID-19 Symptom Diary

All secondary endpoints will be analyzed descriptively and summary statistics will be presented. For time to event endpoints, a Kaplan-Meier plot and the median time to response will be presented along with CIs. For proportion, frequency and incidence endpoints, the number, proportion and difference in proportions along with CIs will be presented. For area under the curve (AUC) endpoints, summary statistics will be presented. Any exploratory statistical testing will be specified in the SAP as appropriate.

Rules for missing data will be specified in the SAP.

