- In order to perform this evaluation Cohort E has been modified to increase enrollment and the Day 14 telephone visit has been changed to an in-person visit to allow for a nasopharyngeal swab to be collected. Relevant changes have been incorporated throughout the protocol including an updated statistical analysis and a cohort specific schedule of activities (Sections 3.1, 3.2, 4.1, 4.2.1, 4.3.1.1, 6 , Figure 1, and Appendix 3)

Additionally, the following changes have been incorporated

- Additional background has been provided regarding the need for COVID-19 treatment options despite new therapies and availability of vaccines (Section 1.1, 3.3.2, 3.3.3).
- New data from the ongoing Phase 1 and Phase 2 studies have been added and the rationales for dose regimen and patient population have been updated accordingly (Sections 1.2, 1.3, 3.3.1.1 , 3.3.1.2, 3.3.2, 5.1.1, and 6)
- A new secondary efficacy endpoint has been added to evaluate the frequency of all cause hospitalizations and death to capture these important outcomes of COVID-19 (Sections 2 and 6.4.2).
- Based on the data from the most recent drug–drug interaction studies the requirement to supplement hormonal contraceptive methods with a barrier method has been removed (Section 4.1.1).
- It has been clarified that the pregnancy test at screening may be performed from urine or serum sample (Sections 4.1.2, 4.5.5, Appendices 1–3)
- It has been clarified that the Cockcroft-Gault formula will be used to calculate creatine clearance as this is standard practice (Sections 4.1.2, 4.5.5, Appendices 1–3)
- The reference to the introduction of the 275 mg tablets after an approved IMPD has been deleted from Section 4.3.1.1 as an IMPD for this formulation has now been approved and the 275 mg has been introduced.
- It has been clarified that paracetamol and non-steroidal anti-inflammatory drugs taken for other reasons other than for COVID-19 symptoms are permitted (Section 4.4.1)
- The cautionary and prohibited therapy sections have been updated with data from recently completed drug–drug interaction studies (Sections 4.4.2, 4.4.3, and Appendix 6).

Additional minor changes have been made to improve clarity and consistency. Substantive new information appears in italics [note: italics not used in Figure 1 or Appendix 3 for readability]. This amendment represents cumulative changes to the original protocol.

TABLE OF CONTENTS

PROTOCOL AMENDMENT ACCEPTANCE FORM	11
PROTOCOL SYNOPSIS	12
1. BACKGROUND	22

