These endpoints will be summarized using descriptive statistics by treatment group, as well as Kaplan-Meier plots where appropriate. The median time to response will be presented along with the 80% CI. For all cohorts, the efficacy time to event endpoints will be described through Day 28 between the AT-527 group and the combined placebo group from all available cohorts using the mITTi population.

A summary of the symptom severity for each symptom in the COVID-19 symptom diary will be provided at baseline, Day 14 and Day 28 for each treatment group and pooled placebo group. Day 14 (morning) assessments are to be used for the Day 14 summary. If the morning sample is missing, the evening sample will be used.

For efficacy time to event endpoints, deaths will be right censored at Day 28. Consequently, for these endpoints, participants censored on Day 28 reflect two different states, death and failure to meet the improvement outcome criterion. Therefore, it is

important to understand the outcome in the context of the number and timing of deaths by treatment group.

Intercurrent events are those that occur after treatment initiation and either preclude observation of the variable or affect its interpretation. Intercurrent events and missing data will be accounted for through censoring rules, as described in [Table 9](#) below.

Table 9 Efficacy Time to Event Censoring

Event	Censor	Date and Time
Death prior to meeting endpoint	Yes	Final timepoint on Day 28
Discontinuation or lost to follow-up up to Day 28 for any reason prior to meeting endpoint	Yes	Last observed COVID-19 symptom diary assessment
Do not meet the endpoint	Yes	Final timepoint on Day 28

Frequency efficacy endpoints include:

- **Frequency of COVID-19-related complications**
 - COVID-19-related complications include: death, hospitalization, radiologically confirmed pneumonia, acute respiratory failure, sepsis, coagulopathy, pericarditis, myocarditis, and cardiac failure.

For frequency efficacy endpoints, the number, proportion and difference in proportions between the AT-527 group and the pooled placebo group from all available cohorts, along with 80% CIs will be presented by treatment group.

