6. SUPPORTING DOCUMENTATION

Appendix 1 Changes to Protocol-Planned Analyses

This section is not applicable, since there are no changes to protocol-planned analyses.

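### The SAP does not list the protocol's secondary endpoint of all-cause hospitalization and death, so followed as written it gives no between-group comparison of all-cause hospitalization

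*Protocol*

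**What the plan says.** Protocol Version 6 lists "Frequency of hospitalizations and death (all cause") as a secondary efficacy endpoint in the synopsis, in Table 1 and in Section 6.4.2.2. Each time it has its own bullet, next to the one for complications: "Frequency of COVID-19-related complications (death, hospitalization, radiologically confirmed pneumonia" and six further conditions). The amendment rationale shows that the addition was deliberate: "A new secondary efficacy endpoint has been added to evaluate the frequency of all cause hospitalizations and death". Section 6.4.2.2 also fixes the form of the output: "For proportion, frequency and incidence endpoints, the number, proportion and difference in proportions along with CIs will be presented". Section 6 assigns all secondary efficacy outcomes to the mITTi population. Section 6.4.2 sets the comparators: pooled placebo for Cohorts A–D, and Cohort E's own placebo for Cohort E.

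SAP Table 1 goes from COVID-19-related complications straight to time to alleviation of an individual symptom. In SAP Section 5.4.2.3 the list headed "Frequency efficacy endpoints include" has one member, defined as follows: "COVID-19-related complications include: death, hospitalization, radiologically confirmed pneumonia, acute respiratory failure, sepsis, coagulopathy, pericarditis, myocarditis, and cardiac failure". SAP Appendix 1 reads: "This section is not applicable, since there are no changes to protocol-planned analyses".

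**The concern.** An endpoint that the current protocol names, and that was added on purpose, has no place in the document from which the tables will be programmed. That document also says it departs from the protocol nowhere, so nothing prompts anyone to notice the gap. What is at stake is the between-group result for admissions of any cause. The complications endpoint does not supply it, because it is limited to events related to COVID-19 and an admission attributed to something else falls outside it.

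The choices that the endpoint needs are also left open: what counts as a hospitalization, over what period, and at what confidence level. They are better settled before anyone sees results by arm.

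**Working it through.** This is mainly a comparison of texts. The plan states no figure for this endpoint that could be reproduced.

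**1. Endpoint lists.** Protocol Table 1 has eight secondary efficacy endpoints: two for alleviation or improvement, two for alleviation, duration of fever, complications, all-cause hospitalization and death, and individual symptoms. SAP Table 1 has seven. The difference, 8 − 7 = 1, is all-cause hospitalization and death. Among frequency endpoints the protocol has two and the SAP has one.

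**2. Is it covered elsewhere in the SAP?**
- *Deaths.* SAP Section 5.4.2.2 lists all deaths and tabulates them by group. This is in the safety population, and no difference in proportions with a confidence interval is promised.
- *Serious adverse events.* These are summarized by group, and Protocol Section 5.2.2 makes inpatient hospitalization a criterion of seriousness. But the SAP has no summary by that criterion. Protocol Section 5.3.5.10 keeps certain admissions for preexisting conditions out of adverse event reporting altogether, and classes admissions for out-of-hours outpatient care as non-serious.
- *Complications.* Hospitalization is one of nine listed conditions, under a COVID-19-related heading.

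None of these compares all-cause hospitalization between groups.

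**3. Which design does the SAP describe?** SAP Section 1.2: 60 + 4 × 40 = 220 patients, with Cohort E having 40 patients randomized 3:1. Protocol Section 3.1: 60 + 3 × 40 + 224 = 404 patients, with Cohort E randomized 1:1. The SAP therefore predates, or was not updated to, the design in which this endpoint appears.

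**4. How informative would the missing result be?** The planned mITTi size in Cohort E is 100 per arm (Protocol Section 6.1). The 112 per arm is the randomized number, 100 / 0.9 = 111.1, rounded up. The documents give no event rate, so I assume the same rate p in both arms, from 1% to 5%. The expected number of patients with an event per arm is 100p. The approximate half-width for the difference is z × √(2p(1 − p)/100).

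| Assumed p | Patients with an event per arm | √(2p(1 − p)/100) | 95% half-width (z = 1.96) | 80% half-width (z = 1.2816) |
|---|---|---|---|---|
| 1% | 1 | 0.0141 | 2.8 points | 1.8 points |
| 3% | 3 | 0.0241 | 4.7 points | 3.1 points |
| 5% | 5 | 0.0308 | 6.0 points | 4.0 points |

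Both levels are shown because SAP Section 5.4 uses 80% for secondary endpoints, while the protocol gives no level for them. It specifies 95% only for the Cohort E primary analysis. With so few events the normal approximation is rough, so the figures show scale only.

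**The case against.** The strongest reply is that this is version lag and not a choice of analysis. The SAP also lacks Cohort E's Day 14 swab, its unpooled placebo comparison and its one-sided 2.5% alpha, so the missing endpoint is one symptom of a SAP not yet aligned with Version 6. Protocol Section 6 requires the SAP to be final only before the end of the study. The protocol itself supplies the population, comparators and output format, and SAP Section 5.4 has a general rule for frequency endpoints that could be applied. Deaths, and most admissions through serious adverse event reporting, will surface in the safety tables.

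Most of this stands, and it rules out several stronger readings:

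- A reader might infer that the sponsor decided to drop the endpoint, or knowingly made a false statement in Appendix 1. The documents do not support that. The statement may have been true of the protocol version for which the SAP was written, which is not among the documents.
- A reader might infer that the trial will report nothing on these outcomes. The safety tables show otherwise in part.
- A reader might infer that complications will be shown only as one merged composite. The SAP does not say so, and it does not rule out showing components.
- A reader might infer that an all-cause endpoint needs no judgement. Here it does: Protocol Section 3.1 allows confinement in clinic on Days 1–7, and someone must decide whether such a stay counts.

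The explanation does not close the gap. The SAP as supplied lists no such result, and the protocol leaves the event definition, observation window and confidence level unstated.

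**Conclusion.** The point holds as a conflict between protocol and SAP that loses one named secondary result, in every cohort, unless the SAP is updated. It should be corrected, but it is modest in weight. The endpoint is descriptive and unpowered, and the primary analysis is unaffected. On the assumed rates of 1% to 5%, Cohort E would show about 1 to 5 patients with an event per arm. The half-width for the difference would be 2.8 to 6.0 points at 95%, or 1.8 to 4.0 at 80%. That is imprecise but reportable. The finding itself rests on the text and does not depend on those rates. It does depend on there being no later SAP version, and none is among the documents.

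**What to change.** Add the endpoint to SAP Table 1 and to the frequency endpoints in Section 5.4.2.3, and correct Appendix 1 so that its statement is true against Version 6. The entry should specify:

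- **Population and count:** mITTi patients with at least one hospitalization or death from first dose to Day 33, with each component also shown separately.
- **Event definition:** in-clinic confinement on Days 1–7 for study logistics is not counted as a hospitalization event. Name the data source for admissions that Protocol Section 5.3.5.10 keeps out of serious adverse event reporting.
- **Comparators:** those of Protocol Section 6.4.2, that is, pooled A–D placebo for Cohorts A–D and Cohort E placebo only for Cohort E. A bare extra bullet in Section 5.4.2.3 would inherit the SAP's pooling of placebo across all available cohorts.
- **Output:** number, proportion and difference in proportions, with the confidence level stated for Cohorts A–D and for Cohort E, and an interval method suited to sparse events.

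The cost is SAP wording and one extra table, with no new patients. If the SAP is to be aligned with Version 6 as a whole, this belongs in the same revision.
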